## SYNOPSIS

Title	A Phase 2 Trial of Regorafenib as a Single Agent in Advanced and Metastatic Biliary Tract Carcinoma Patients Who Have Failed First-line Chemotherapy
Clinical study phase	Phase 2 single arm
Study objective(s)	
Primary objective:
 
To evaluate the progression-free survival (PFS) of patients with advanced or metastatic biliary cancer receiving regorafenib following the failure of first-line chemotherapy.
 
Secondary objectives:
 
 
• Overall response (OR), including complete and partial response, and disease Control rate (DCR).
 
• Overall survival (OS)
 
• Measurable changes in biomarkers [CA19-9 and CEA], in patients that were elevated at the time of study entry.
 
• Evaluation of safety and associated toxicities
 

Background treatment	Advanced and metastatic biliary tract carcinoma who have failed first-line chemotherapy.
Indication	Biliary Tract Carcinoma
Diagnosis and main criteria for inclusion	
 
• Histologically or cytologically confirmed diagnosis of biliary tract adenocarcinoma/cholangiocarcinoma; pathologic confirmation may be from the primary or a metastatic site
 
• Must have locally advanced or distant metastatic disease that is not surgically curable
 
• Failed first-line chemotherapy.
 
• Age <math>\geq 18</math> years.
 
• Life expectancy of at least 12 weeks (3 months).
 
• Performance status <math>\leq 1</math>
 
• Adequate liver, kidney, and bone marrow function as assessed by the following laboratory requirements: 
 
➢ Total bilirubin <math>\leq 3.0 \times</math> the upper limit of normal (ULN)
 
➢ Alanine aminotransferase (ALT) and aspartate aminotransferase (AST) <math>\leq 5.0 \times</math> ULN
 
➢ Alkaline phosphatase limit <math>\leq 2.5 \times</math> ULN (<math>\leq 5.0 \times</math> ULN for subjects with intrahepatic involvement of their cancer)
 
➢ Serum creatinine <math>\leq 1.5 \times</math> the ULN
 
➢ International normalized ratio (INR)/partial thromboplastin time (PTT) <math>\leq 1.5 \times</math> ULN.
 
 
 

Study design	Patients with advanced and metastatic biliary tract adenocarcinoma (cholangiocarcinoma) who had been treated with and failed first-line chemotherapy will be treated with regorafenib (120 mg) orally once daily 21 days (3 weeks) on and 7 days (1 week) off in the 28-day (4-week) cycle.
Type of control	Single arm uncontrolled

Number of subjects	Maximum of 37 patients.
Plan for statistical analysis	
There will be no stratification. OR will be estimated at end of trial with 95% exact binomial confidence intervals. PFS and OS will be estimated by the Kaplan-Meier method, with appropriate 90% confidence intervals. Toxicity events will be tabulated. Change in CA19-9 and CEA will be characterized by their mean changes, with a nonparametric CDF-based 90% confidence interval. The study will have 83% power (using a one-sided test at <math>\alpha=0.10</math>) to reject the null hypothesis (PFS<2.0 months) if the true median PFS is at least 3.5 months.

Schema:

## 1. OBJECTIVES

### 1.1 Primary Objectives

To evaluate the progression-free survival (PFS) of patients with advanced or metastatic biliary tract carcinoma (cholangiocarcinoma) receiving rafrafenib following the failure of first-line chemotherapy.

### 1.2 Secondary Objectives

- Overall response rate (ORR), including complete and partial response, and disease control rate (DCR)
- Overall survival (OS)
- Measurable changes in biomarkers [CA19-9 and CEA], in patients that were elevated at the time of study entry.
- Evaluation of safety and associated toxicities

## 2. BACKGROUND

### 2.1 Study Disease(s)

Biliary tract adenocarcinoma (Cholangiocarcinoma, gallbladder carcinoma) is a relatively rare but aggressive neoplasm. There are about 7,000-10,000 new cases diagnosed per year in the United States. The incidence of intrahepatic cholangiocarcinoma is rising globally, and this rising rate has not been associated with an increase in the proportion of early stage disease. The five-year overall survival for advanced disease is only about 5%. It is also the second most common primary hepatic tumor but more lethal than HCC. Treatment outcomes and survival have improved little over the past three decades—a period in which successful new treatments have increased patient survival for many other cancers.

As with most solid tumors, surgical resection represents the only curative therapy. However, the majority of patients with cholangiocarcinoma present with unresectable or metastatic disease. Currently, for these patients, first-line therapy consists of systemic chemotherapy with the combination of gemcitabine and cisplatin. Despite a described response rate of over 80%, median overall survival remained poor at 11.7 months. Other gemcitabine-based and flouopyrimidine-based chemotherapy regimens have been also used. In selected patients, local-regional therapy e.g. chemoembolization with gemcitabine-based treatment has been applied as well. With all of these regimens, efficacy was limited with significant associated morbidities. There is no standard 2nd line therapy besides Phase 2 data. The mPFS (or TTP) of 2nd-line varies around 1.6-2.3 months (see refs: Oh SY, et al and Lee S, et al), and mOS varies between 4-6 months. More effective therapies are definitely needed with better understanding of the mechanisms of this disease and therapy to treat it.

Several signaling pathways have been identified that might play a role in the development of

cholangiocarcinoma. Over-expression of p53 has been found in 20 to 30 percent of tumors. BRAF mutations were seen in approximately 22 percent of intrahepatic cholangiocarcinomas. VEGF was also found to be overexpressed in a majority of patients with intrahepatic and extrahepatic cholangiocarcinoma. In several studies, abnormal expression of K-ras was seen in 45 to 54 percent of intrahepatic cholangiocarcinomas, and 10 to 15 percent of extrahepatic cholangiocarcinomas. In one study, the incidence of K-ras gene mutations in patients with lymph node metastasis was seen to be higher than that in patients without, and patients with K-ras gene mutations showed a statistically significant worse survival rate than those without such mutations.

## 2.2 Regorafenib

Regorafenib is a novel diphenylurea oral multikinase inhibitor of angiogenic (VEGFR1-3, TIE2), stromal (PDGFR- $\beta$ , FGFR1), and oncogenic kinases (KIT, RET, RAF) with potent preclinical antitumor activity and long-lasting anti-angiogenic activity as measured by dynamic contrast enhanced (DCE) – magnetic resonance imaging (MRI) (1).

Regorafenib potently inhibits angiogenic kinases VEGFR 1-3, TIE2, PDGFR- $\beta$ , and fibroblast growth factor receptor 1(FGFR1) in biochemical (IC50 between 4 and 311 nanomolar [nM]) and cellular (IC50 between 3 and  $\sim$ 200 nM) kinase phosphorylation assays. The VEGF, TIE2 and PDGF receptors are relevant to tumor angiogenesis (2, 3). PDGF receptors may also play a role in patients with chronic myeloproliferative cancers (4).

Furthermore, it potently inhibits mutant oncogenic kinases KIT (cellular IC50 c-KITK642E = 22 nM) and RET (cellular IC50 RETC634W  $\sim$ 10 nM), which play a role in human gastrointestinal stromal and thyroid cancers, respectively, and B-RAF, a member of the *RAS/RAF/MEK/ERK* signaling pathway (biochemical IC50 of wt B-RAF = 28nM and of B-RAFV600E = 19nM). In addition, it biochemically inhibits Raf-1 (IC50 = 2.5 nM) and the p38 MAPK (IC50 = 24 nM) (1).

### 2.2.1 Preclinical

In vivo, regorafenib exhibited anti-angiogenic and anti-proliferative effects in human colon and breast xenografts as demonstrated by a reduction in microvessel area, reduced Ki-67 staining, and reduced pERK1/2 staining in tissue sections from tumor xenografts, and dose-dependent inhibition of growth in multiple xenograft models (breast, colon, renal, NSCLC, melanoma, pancreatic, thyroid, ovarian). (1) Immunohistochemical ex-vivo studies with a phospho-specific monoclonal anti-ERK 1 / 2 antibody demonstrated inhibition of the MAPK pathway five days after treatment with regorafenib in 2 of 3 tumor models examined (MDA-MB 231 and BxPC-3), but not in NSCLC (H460).

In addition, all tested human tumor xenografts (MDA-MB-231, H460, BxPC-3 and Colo-205) demonstrated a significant reduction in new blood vessels by histomorphometry as detected in tumor samples using a murine CD31 antibody. (1) These data suggest that regorafenib can target the tumor cell MAPK pathway (tumor cell survival) and tumor vasculature in some but not all tumors.

## 2.2.2 Clinical experience

Two Phase 3 global randomized studies have evaluated the efficacy of regorafenib. The CORRECT (Patients with metastatic colorectal cancer treated with regorafenib or placebo after failure of standard therapy) trial is an international, multicenter, randomized, double-blind, placebo-controlled study with 114 centers in 16 countries. Patients with documented metastatic colorectal cancer and progression during or within 3 months after the last standard therapy were randomized (in a 2:1 ratio; stratified by previous treatment with anti-VEGF therapy, time from metastatic disease diagnosis, and geographical area) to receive oral regorafenib, 160 mg once daily, plus best supportive care (BSC) or placebo plus BSC, with 3 weeks on and 1 week off as a cycle. The primary endpoint was overall survival. From April 30, 2010 to March 22, 2011, there were 1052 patients screened, 760 patients were randomized to receive regorafenib (n=505) or placebo (n=255); 753 patients initiated treatment (regorafenib n=500; placebo n=253). The primary endpoint of overall survival was met at a preplanned interim analysis. Median overall survival was 6.4 months in the regorafenib treatment arm versus 5.0 months in the placebo arm (HR of 0.77; 95% CI 0.64–0.94; one-sided p=0.0052). Treatment-related adverse events occurred in 465 (93%) patients assigned regorafenib and in 154 (61%) of those assigned placebo. The most common adverse events of grade three or higher related to regorafenib were hand-foot skin reaction (83 patients, 17%), fatigue (48, 10%), diarrhea (36, 7%), hypertension (36, 7%), and rash or desquamation (29, 6%).

The efficacy and safety of regorafenib were examined in the Phase 3 GRID trial in patients with gastrointestinal stromal tumors (GISTs) who had exhausted all other treatment options. The study was conducted at 57 hospitals in 17 countries. Patients with histologically confirmed, metastatic or unresectable GIST, with failure of at least previous imatinib and sunitinib were randomized in a 2:1 ratio (stratified by treatment line and geographical region) to receive either oral regorafenib, 160 mg daily, plus best supportive care (BSC) or placebo plus BSC, 3 weeks on and 1 week off as a cycle. 240 patients were screened and 199 were randomized to receive regorafenib (n=133) or matching placebo (n=66). Median PFS per independent blinded central review was 4.8 months (IQR 1.4–9.2) for regorafenib and 0.9 months (0.9–1.8) for placebo (HR 0.27, 95% CI 0.19–0.39; p<0.0001). After progression, 56 patients (85%) assigned placebo crossed over to regorafenib. The overall disease control rate combining partial responses with durable stable disease for at least 12 weeks was 53% with regorafenib compared with 9% in the control group. Drug-related adverse events were reported in 130 (98%) patients that had regorafenib and 45 (68%) patients assigned to placebo. The most common regorafenib-related adverse events of grade 3 or higher were hypertension (31 of 132, 23%), hand-foot skin reaction (26 of 132, 20%), and diarrhea (seven of 132, 5%).

Based on the facts of multiple pathways involvement in cholangiocarcinoma tumor genesis, including EGFR, Ras, Raf, VEGFR, and PDGFR, with evidence of overexpression of these proteins associated with tumor stage, prognosis and response to therapy. Multikinase inhibitor targeting multiple tumor pathways agent as regorafenib should be the ideal candidate for evaluating the anti-cancer activity for the disease as cholangiocarcinoma. More importantly, regorafenib likely holds promise in this disease setting with known effectiveness either as a single agent or in combination with cytotoxic chemotherapy agents in multiple solid tumors as above and the toxicity profile.

## 2.3 Rationale

As noted, multiple pathways, including EGFR, Ras, Raf, VEGFR, and PDGFR appear to be involved in cholangiocarcinoma tumor genesis. Overexpression of these proteins has been shown to be associated with tumor stage, prognosis, and response to therapy. However, therapies targeting a single pathway have shown no clear benefit. A number of Phase 2 trials have been completed, or are underway, studying agents targeted to EGFR or VEGF – both as monotherapy and in combination with chemotherapy. These have shown varying increases in response rate, but have not found marked increases in progression-free or overall survival. This suggests that inhibition of multiple pathways simultaneously may be needed. Regorafenib, is an oral multikinase inhibitor targeting multiple tumor pathways, which has showed effectiveness as a single agent in multiple solid tumors.

## 3. PATIENT SELECTION

### 3.1 Eligibility Criteria

- Histologically or cytologically confirmed diagnosis of biliary tract adenocarcinoma/ cholangiocarcinoma (including primary intra- and extrahepatic diseases); pathologic confirmation may be made from the primary or a metastatic site.
- Must have locally advanced or distant metastatic disease that is not surgically curable.
- Failed first-line chemotherapy (including systemic and local-regional therapy).
- Age  $\geq$  18 years
- Life expectancy  $\geq$  12 weeks (3 months)
- Performance status ECOG  $\leq$  1
- Adequate liver, kidney, and bone marrow function as assessed by the following laboratory requirements:
  - Total bilirubin  $\leq$  3.0 x the upper limits of normal (ULN) (biliary stenting or percutaneous biliary drainage are allowed for cancer related biliary obstruction)
  - Alanine aminotransferase (ALT) and aspartate aminotransferase (AST)  $\leq$  5.0 x ULN
  - Alkaline phosphatase limit  $\leq$  2.5 x ULN ( $\leq$  5.0 x ULN for subjects with intrahepatic involvement of their cancer)
  - Serum creatinine  $\leq$  1.5 x the ULN
  - International normalized ratio (INR)/partial thromboplastin time (PTT)  $\leq$  1.5 x ULN. (Patients who are therapeutically treated with an agent such as warfarin or heparin will be allowed to participate provided that no prior evidence of underlying abnormality in coagulation parameters exists. Close monitoring of at least weekly evaluations will be performed until INR/PTT is stable based on a measurement that is pre-dose as defined by the local standard of care).
  - Platelet count  $\geq$  75,000 /mm^3,

- Hemoglobin (Hb)  $\geq$  9 g/dL,
- Absolute neutrophil count (ANC)  $\geq$  1500/mm^3.
- Blood transfusion to meet the inclusion criteria will not be allowed.
- Women of childbearing potential must have a negative serum pregnancy test performed within 7 days prior to the start of study drug. Post-menopausal women (defined as no menses for at least 1 year) and surgically sterilized women are not required to undergo a pregnancy test.
- Patients (men and women) of childbearing potential must agree to use Double Barrier method of birth control beginning at the signing of the ICF until at least 3 months after the last dose of study drug.
- Patients must be able to swallow and retain oral medication.
- Patients must be able to understand and be willing to sign the written informed consent form. A signed informed consent form must be appropriately obtained prior to the conduct of any trial-specific procedure.

### **3.2 Exclusion Criteria**

- Previous assignment to treatment during this study. Subjects permanently withdrawn from study participation will not be allowed to re-enter study.
- Uncontrolled hypertension (systolic pressure  $\geq$ 140 mm Hg or diastolic pressure  $\geq$ 90 mm Hg on repeated measurement) despite optimal medical management.
- Active or clinically significant cardiac disease including:
  - Congestive heart failure – New York Heart Association (NYHA) > Class II.
  - Active coronary artery disease.
  - Cardiac arrhythmias requiring anti-arrhythmic therapy other than beta blockers or digoxin.
  - Unstable angina (angina symptoms at rest), new-onset angina within 3 months before randomization, or myocardial infarction within 6 months before randomization.
- Evidence or history of bleeding diathesis or coagulopathy.
- Any hemorrhage or bleeding event  $\geq$  Grade 3 within 4 weeks prior to prior to registration.
- Patients with thrombotic, embolic, venous, or arterial events, such as cerebrovascular accident (including transient ischemic attacks) deep vein thrombosis or pulmonary embolism within 6 months of the study registration.
- Previous exposure to VEGF inhibitor(s),
- Patients with any previously untreated or concurrent cancer that is distinct in primary site or histology from biliary tract cancer except cervical cancer in-situ, treated basal cell carcinoma, or superficial bladder tumor. Patients surviving a cancer that was curatively treated and without evidence of disease for more than 3 years prior to registration are

allowed. All cancer treatments must be completed at least 3 years prior to prior to registration).

- Patients with phaeochromocytoma.
- Known history of human immunodeficiency virus (HIV) infection or current chronic or active hepatitis B or C infection requiring treatment with antiviral therapy.
- Ongoing infection > Grade 2.
- Symptomatic metastatic brain or meningeal tumors.
- Presence of a non-healing wound, non-healing ulcer, or bone fracture.
- Renal failure requiring hemo- or peritoneal dialysis.
- Dehydration Grade  $\geq 1$
- Patients with seizure disorder requiring medication.
- Proteinuria  $\geq$  Grade 3 ( $> 3.5$  g/24 hours, measured by urine protein: creatinine ratio on a random urine sample).
- Active signs and symptoms of interstitial lung disease pleural effusion or ascites that causes respiratory compromise ( $\geq$ Grade 2 dyspnea).
- History of organ allograft (including corneal transplant).
- Known or suspected allergy or hypersensitivity to any of the study drug classes.
- Any malabsorption condition.
- Women who are pregnant or breast-feeding.
- Any condition which, in the investigator's opinion, makes the subject unsuitable for trial participation.
- Substance abuse, medical, psychological or social conditions that may interfere with the subject's participation in the study or evaluation of the study results.
- Concurrent anti-cancer therapy (chemotherapy, radiation therapy, surgery, immunotherapy, biologic therapy, or tumor embolization) other than study treatment regorafenib. However, the palliative XRT to non-targeted lesions is allowed.
- Prior use of regorafenib.
- Concurrent use of another investigational drug or device therapy (i.e., outside of study treatment) during, or within 28 days prior to registration
- Major surgical procedure, open biopsy, or significant traumatic injury within 28 days prior to registration (biliary stenting or percutaneous biliary drainage are not included).
- Use of any herbal remedy (e.g. St. John's Wort [Hypericum perforatum])

### 3.3 Withdrawal of patients from study treatment

Patients **must be withdrawn from the study treatment** for the following reasons:

- Patients withdraw consent for study treatment and study procedures. A patient must be removed from the trial at his/her own request or at the request of his/her legally acceptable representative. At any time during the trial and without giving reasons, a subject may decline to participate further. The patient will not suffer any disadvantage as a result.
- Pregnancy
- Subject is lost to follow-up
- Disease Progression
- Death

Patients **may be** withdrawn from the study treatment for the following reasons:

- The patient is non-compliant with study drug, trial procedures, or both; including the use of anti-cancer therapy not prescribed by the study protocol.
- If, in the investigator's opinion, continuation of the trial would be harmful to the patient's well-being.
- Severe allergic reaction to regorafenib (such as exfoliative erythroderma or Grade 3 or 4 hypersensitivity reaction).
- The development of a second cancer.
- Development of an intercurrent illness or situation which would, in the judgment of the investigator, significantly affect assessments of clinical status and trial endpoints.
- Deterioration of ECOG performance status to 4.
- Use of illicit drugs or other substances that may, in the opinion of the investigator, have a reasonable chance of contributing to toxicity or otherwise skewing trial result.

In all cases, the reason for removal from study must be recorded in the research data base and in the patient's medical records.

Details for the premature termination of the study as a whole (or components thereof [e.g. centers, treatment arms, dose steps]) are provided in Section 12.3 (Premature termination of the study).

### **3.4 Screen Failures/Dropouts**

A patient who discontinues study participation prematurely for any reason is defined as a “dropout” if the patient has: already been registered, administered at least one dose of study drug.

A patient who, for any reason (e.g. failure to satisfy the selection criteria; withdraws consent), prior to receiving first dose of study drug will be regarded a “screening failure”.

### **3.5 Replacement**

No withdrawn patients will be replaced, 'Drop out patients may be replaced.

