## **4. TREATMENT PLAN**

Patients with advanced and metastatic biliary tract adenocarcinoma (cholangiocarcinoma) who had been treated and failed first-line chemotherapy, ECOG PS 0-1, and adequate liver, kidney and bone marrow function will be treated with regorafenib (160 mg) orally once daily for 21 days on and 7 days off in a 28-day cycle. Tissue specimens collected at diagnosis may be submitted for molecular analyses or other studies.

A maximum of 37 patients will be enrolled.

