#### 10.1.1 Definitions

Evaluable for toxicity. All patients will be evaluable for toxicity from the time of their first treatment with regorafenib.

Evaluable for objective response. Only those patients who have measurable disease present at baseline, have received at least one cycle of therapy, and have had their disease re-evaluated will be considered evaluable for response. These patients will have their response classified according to the definitions stated below. (Note: Patients who exhibit objective disease progression prior to the end of cycle 1 will also be considered evaluable.)

Evaluable Non-Target Disease Response. Patients who have lesions present at baseline that are evaluable but do not meet the definitions of measurable disease, have received at least one cycle of therapy, and have had their disease re-evaluated will be considered evaluable for non-target disease. The response assessment is based on the presence, absence, or unequivocal progression of the lesions.

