#### **12.1.2 Secondary objectives**

- Overall response rate (ORR), including complete and partial response. The ORR at four months will be estimated with an exact 90% binomial confidence interval.
- Overall survival (OS). The overall survival function will be estimated by the Kaplan-Meier method, with a 90% confidence interval.
- DCR (disease control rate) as ORR plus stable disease (SD)
- Measurable changes in biomarkers (CA19-9 and CEA), in patients that were elevated at the time of registration. The means and standard deviation of both markers will be estimated at before and after treatment. The null hypothesis of no treatment effect will be tested using a paired-comparison t-test ( $\alpha=0.10$ ), or a rank sum test if there is evidence of significant non-normality in the differences.
- Evaluation of safety and associated toxicities. Toxicities will be tabulated by grade and type.

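### Replacement rules conflict for a dosed patient who withdraws consent or is lost to follow-up, and the response-evaluability rules leave unassessed treated patients out of ORR and DCR

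*Combined protocol and SAP*

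**What the plan says.** All references are to the combined protocol and SAP.

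**Replacement.** Section 3.5 states: "No withdrawn patients will be replaced, 'Drop out patients may be replaced". Section 3.4 supplies one of the two terms: "A patient who discontinues study participation prematurely for any reason is defined as a" dropout, provided the patient was registered and took at least one dose. Patients who leave before a first dose are screening failures. Section 3.3 supplies the other term by listing reasons for withdrawal. Two of the mandatory ones are consent withdrawn for both treatment and procedures ("A patient must be removed from the trial at his/her own request") and "Subject is lost to follow-up". Section 4 sets the size: "A maximum of 37 patients will be enrolled".

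**Response population.** Section 10.1.1 says that only patients who have measurable disease at baseline, "have received at least one cycle of therapy, and have had their disease re-evaluated will be considered evaluable for response". Its one exception is that "Patients who exhibit objective disease progression prior to the end of cycle 1 will also be considered evaluable". A parallel definition for non-target disease carries the same cycle and re-evaluation conditions. Section 12.1.2 states "The ORR at four months will be estimated with an exact 90% binomial confidence interval" and defines DCR as ORR plus stable disease. It names a denominator for neither. For safety, by contrast, Section 6 counts everyone who took a dose.

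**The concern.** On replacement, the choice of label decides whether a further patient may be enrolled in place of one already dosed. The label is applied after dosing, in an open-label single-arm trial, and the text supports either choice for two categories of patient. Nothing says that a replaced patient stays in the efficacy analyses.

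On response, the first scheduled re-evaluation comes after two 28-day cycles (Section 10.1), close to the 2.0-month null median PFS. Some patients may die or decline before that scan. A patient never re-evaluated has no recorded response or stable disease, so removing that patient shrinks the denominator and leaves the numerator as it was. The reported ORR and DCR would then describe those who stayed long enough to be scanned, not those who were treated.

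**Working it through.** **Step 1: do the two labels overlap?**

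| Dosed patient who | Section 3.3 | Section 3.4 | Section 3.5 |
|---|---|---|---|
| withdraws consent to treatment and procedures | withdrawn, removed from the trial | dropout | barred and allowed |
| is lost to follow-up | withdrawn | dropout | barred and allowed |
| only stops treatment and stays in follow-up | withdrawn from treatment | not a dropout | barred, no conflict |

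The conflict is confined to the first two rows.

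**Step 2: the plan's own figure.** The plan gives no expected ORR, DCR or leaver rate. The only stated figure that rests on 37 patients is the 83% power for PFS (Section 12.2). It reproduces, assuming exponential PFS. Survival at 2 months under a 3.5-month median is 0.5^(2/3.5) = 0.673, and Φ((0.673 − 0.5)/√(0.673 × 0.327/37) − 1.2816) = 83.2%. It is not in dispute here.

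**Step 3: effect of dropping patients never re-evaluated.** Let n be treated patients with measurable disease, x those with the outcome, and k those never re-evaluated, counted as failures in the all-treated rate. Then

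- all-treated rate = x/n
- evaluable-only rate = x/(n − k) = (x/n) × n/(n − k)

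All counts below are assumptions. Measurable disease is not an eligibility requirement, so n = 37 and n = 30 are both shown. Intervals are exact 90%, the level in Section 12.1.2.

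| Outcome | k = 0 | k = 3 | k = 5 |
|---|---|---|---|
| DCR, n = 37 | 20/37 = 54.1% (39.4–68.2) | 20/34 = 58.8% (43.3–73.1) | 20/32 = 62.5% (46.4–76.7) |
| ORR, n = 37 | 4/37 = 10.8% (3.8–23.1) | 4/34 = 11.8% (4.1–24.9) | 4/32 = 12.5% (4.4–26.4) |
| DCR, n = 30 | 16/30 = 53.3% (37.0–69.2) | 16/27 = 59.3% (41.7–75.2) | 16/25 = 64.0% (45.6–79.8) |
| ORR, n = 30 | 3/30 = 10.0% (2.8–23.9) | 3/27 = 11.1% (3.1–26.3) | 3/25 = 12.0% (3.4–28.2) |

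For n = 37 the multiplier is 37/34 = 1.09 or 37/32 = 1.16.

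**Step 4: can the rule also push the rate down?** Section 10.1.1 requires a completed cycle as well as a re-evaluation. A patient who stops during cycle 1 and has stable disease on the end-of-treatment scan (Section 9) is excluded despite having disease control. If j of the k excluded patients have disease control, the evaluable-only rate is (x − j)/(n − k). This exceeds x/n only when j/k < x/n. With x/n = 20/37 and k = 3:

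- j = 0: 20/34 = 58.8%, higher
- j = 1: 19/34 = 55.9%, higher
- j = 2: 18/34 = 52.9%, lower than 54.1%

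The direction therefore depends on who is excluded.

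**The case against.** The strongest reply on replacement is that Section 3.3 concerns treatment and Section 3.4 concerns participation, so the labels do not compete. That holds for patients who only stop treatment. It does not hold for the two categories at issue, because withdrawing consent to procedures or being lost to follow-up ends participation as well. It is also fair that Section 4 speaks of a maximum enrolled. Read plainly, replacements already count within the 37, so a reader should not infer that the label could enlarge the trial.

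On response, the documents do limit the loss. Documented progression in cycle 1 keeps a patient evaluable, Section 9 schedules an end-of-treatment scan, and a note in Section 10.1.4.3 asks that progression still be sought after treatment stops. These reduce the number dropped. They do not cover a patient who dies, deteriorates or leaves with no scan at all.

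Two stronger readings are tempting and fail. One is that the bias is always favourable; Step 4 shows otherwise. The other is that the measurable-disease rule is the only response-population rule; Section 10.1.1 has a non-target counterpart, and Section 10.1.4.3 has a response table for those patients.

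Finally, ORR and DCR are secondary, with no test or decision rule, and the illustrated shifts lie inside the confidence intervals. That limits the importance of the point but does not supply a denominator.

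**Conclusion.** Both parts stand, as corrections worth making to the wording and not as a threat to the primary analysis.

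The replacement conflict is certain on the text and affects two categories of dosed patient.

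The response rules, applied as written, inflate ORR and DCR by n/(n − k) relative to a rate that counts never-assessed treated patients as failures. On assumed losses of 3 or 5 of 37, that is about 5 to 8 points for DCR and 1 to 2 points for ORR. The net bias is expected to be upward, since death and deterioration before a scan are likely reasons for exclusion. It is not certain, because of the one-cycle condition and because the true status of an unassessed patient is unknown.

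A reader might infer that the PFS test is compromised too. The documents do not support that as a consequence of these rules. Sections 10.1.6 and 12.1.1 exclude no treated patient, Sections 4.5 and 9 plan follow-up to death or study closure, and death is an event. Informative censoring of early leavers is a separate matter that neither the replacement wording nor a denominator rule would change. For PFS, one sentence on inclusion is enough.

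**What to change.** - **Sections 3.3–3.5:** define *withdrawn* and *dropout* so that no patient fits both. State that any replacement counts within the maximum of 37 enrolled and that every dosed patient stays in the efficacy analyses, replaced or not. Not replacing dosed patients at all is the simplest way to achieve this, but it removes a permission the sponsor wrote in. Clear definitions with full retention would also do.
- **Sections 10.1.1 and 12.1.2:** make the primary denominator for ORR and DCR all treated patients with measurable disease at baseline, whatever number of cycles they completed. Count those with no post-baseline assessment as non-responders without disease control, and classify all others by their scans. Report patients with only non-measurable disease separately, using the table for them in Section 10.1.4.3. Keep the evaluable-only rate as supportive.
- **Section 12.1.1:** add one sentence that PFS includes all dosed patients.

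The cost is wording only, with no extra patients or visits. The downside is that ORR and DCR become slightly less favourable.
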